Aim 3 (qualitative): We will conduct qualitative analysis of interview data. Interview audio files will be transcribed verbatim. Data from qualitative interviews will be used to develop a deeper understanding of the barriers/facilitators to health behavior change experienced by older Veterans with psychosis. Data will also be used to add context to quantitative findings, particularly with questions related to "how" and "why" the intervention did or did not work.

Aim 4 (quantitative): We will use blocked entry regression analyses to examine relative contributions of RBANS score, PANSS negative symptom subscale, BDI total, UPSA-Brief score, and MPPT score to the prediction of each of the SLOF domains. Age, gender, BMI, and Charlson Comorbidity Index will be entered as covariates.

ID: VIEW4E02806052800
Name: v2_Sample Size and Data Analysis

Sharing of Results

1 * Describe whether results (study results or individual subject results, such as results of investigational diagnostic tests, genetic tests, or incidental findings) will be shared with subjects or others (e.g., the subject's primary care physicians) and if so, describe how it will be shared:

In Aims 2 and 3, participants will undergo a physical, exercise tests, and/or tests of physical function. Participants will be advised of findings from the screening physicals and exercise tests that have a direct effect on their health. With a participant's permission, these results will be shared with his/her doctor. These findings may be shared through a note or consult in the electronic medical record. The screening may include a blood draw. Lab results will be posted in participants' electronic medical records.

For Aims 2, 3, and 4, if clinically indicated during study participation, research staff may ask permission from participants to speak with members of their VA treatment team or with other VA treatment providers, to facilitate clinically appropriate referrals and care coordination.

*ID: VIEW4E02808CBD800
Name: v2_Sharing of Results*

Psychological/Behavioral/Educational Methods & Procedures

You indicated on the "Type of Research" page that your study involves a psychological/behavioral/educational method or procedure such as a survey, questionnaire, interview, or focus group.

1 * Select all behavioral methods and procedures which apply to this study:

- Surveys/questionnaires
- Key informant or semi-structured individual interviews
- Focus groups or semi-structured group discussions
- Audio or video recording/photographing
- Educational tests or normal educational practices (education instructional strategies, techniques, curricula, or classroom management methods)
- Individual or group behavioral observations
- Psychosocial or behavioral interventions
- Neuropsychological or psychophysiological testing
- Deception
- Other psychosocial or behavioral procedures

ID: VIEW4E09416F57800

Name: v2_Psychological/Behavioral/Educational Methods and Procedures

Surveys/Questionnaires

You indicated that this study involves surveys and/or questionnaires.

If you uploaded a separate research protocol document in the 'Research Protocol' page, cite the applicable section and page numbers from that document in the answer boxes below.

1 * List all questionnaires/surveys to be used in the study, including both standardized and non-standardized assessments:

MIRECC Demographic Form
 International Physical Activity Questionnaire (IPAQ)
 Exercise Self-Efficacy Scale (EXSE)
 Barriers Self-Efficacy Scale
 Social Support for Exercise Survey
 Veterans RAND 36-Item Health Survey (VR-36)
 World Health Organization Disability Assessment Schedule 2.0 (Clinician-Rated WHO-DAS)
 Life Space Questionnaire (LSQ)
 Geriatric Depression Scale- Long Form (GDS)
 Level of Functioning Assessment (SLOF)
 World Health Organization Disability Assessment Schedule (WHO-DAS)
 BMI Form

2 * Upload a copy of all questionnaires/surveys:

Name	Created	Modified Date
BMI Form(0.01)	11/8/2019 12:10 PM	11/8/2019 12:10 PM
WHO-DAS 2.0(0.03)	10/24/2016 12:22 PM	7/30/2019 2:34 PM
MIRECC Demographic Form 5.1.2019(0.02)	10/24/2016 12:21 PM	5/1/2019 3:06 PM
WHO-DAS(0.01)	1/24/2019 8:23 AM	1/24/2019 8:23 AM
GDS Long Form(0.01)	10/18/2018 1:03 PM	10/18/2018 1:03 PM
Level of Functioning Assessment (SLOF)(0.01)	9/14/2018 3:17 PM	9/14/2018 3:17 PM
LSQ(0.01)	9/12/2018 3:35 PM	9/12/2018 3:35 PM
VR-36(0.01)	10/24/2016 12:22 PM	10/24/2016 12:22 PM
Social Support for Exercise(0.01)	10/24/2016 12:22 PM	10/24/2016 12:22 PM
Barriers Self-Efficacy(0.01)	10/24/2016 12:22 PM	10/24/2016 12:22 PM
EXSE(0.01)	10/24/2016 12:21 PM	10/24/2016 12:21 PM
IPAQ(0.01)	10/24/2016 12:21 PM	10/24/2016 12:21 PM

3 * What is the total length of time that each survey is expected to take?

MIRECC Demographic Form- 5 minutes
 International Physical Activity Questionnaire- 15 minutes
 Exercise Self-Efficacy Scale- 5 minutes
 Barriers Self-Efficacy Scale- 5 minutes
 Social Support for Exercise Survey- 5 minutes
 Veterans RAND 36-Item Health Survey- 15 minutes
 Life Space Questionnaire - 5 minutes
 Geriatric Depression Scale- Long Form - 5 minutes
 World Health Organization Disability Assessment Schedule - 10 minutes
 BMI Form - 5 minutes

Clinician-rated measure
 Level of Functioning Assessment - 15 minutes
 World Health Organization Disability Assessment Schedule 2.0 (clinician rated) - 5 minutes

4 * Are any of the questions likely to cause discomfort in participants or cause harm if their confidentiality were breached? (i.e., Illegal activities)

Yes No

5 * Do any questions elicit information related to the potential for harm to self or others?

Yes No

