8) Follow-up brief interviews (30-60 minutes). At the end of ~24 weeks, Veteran participants will be contacted by phone for an audio-recorded phone interview, assessing acceptability and perceived utility of the maintenance phase of the PEER intervention. This interview may be conducted in person if the Veteran prefers.

If a participant expresses to study staff that he or she is having difficulty attending study appointments due to lack of transportation then a bus token, or equivalent travel voucher, will be offered to the participant if available.

9) Qualitative interviews of PEER facilitators (60-120 minutes) The group facilitators will be invited to complete an optional qualitative interview about their thoughts, feelings, and experiences in training and delivering the intervention. If an eligible facilitator agrees to participate they may be invited to complete additional, optional interviews throughout the course of the study.

*Aim 3: Veteran participants (n=20) will be recruited for a pilot randomized controlled trial of PEER. All participants will have access to supervised fitness training at the SERC at the Baltimore VA Medical Center or the Loch Raven VA Medical Center. Participants will be randomized to receive group-based peer coaching (the PEER condition) or individual support from non-peer staff (the enhanced supervised fitness training condition, ESFT).

1) Consent (60 minutes): Informed consent may be completed virtually by phone/video, or in person. Research staff will obtain informed consent prior to any study activities.

2) Screening: Screening procedures will include an extensive chart review by GRECC staff and a GRECC medical provider, with sign-off on eligibility by the medical provider. Current medications, medical diagnoses, and height and weight information will be recorded from the chart. On a case-by-case basis, participants may be asked to complete a history and physical (remote or in person, 30 minutes) with a GRECC medical provider. They may also be asked to complete a fasted blood draw and/or a glucose test, at the discretion of the GRECC medical provider, to determine eligibility. The fasting blood draw (approximately 2 tablespoons) would measure electrolyte, hormone, lipid, and cholesterol levels and/or determine an average blood sugar level over the past 3 months.

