5) Supervised fitness training sessions: Eligible participants will be provided an exercise prescription for 60 minutes of supervised fitness training, three times a week, tailored to their physical profiles and consistent with general exercise recommendations for older adults. They will be invited to attend the Baltimore VA or Loch Raven VA SERC facilities to complete their prescriptions, under the supervision of GRECC exercise physiologists, by appointment, for the duration of the 24-week trial. Physiologists will complete tests of physical function during select gym visits (baseline, 12 weeks, and 24 weeks post-randomization).

6) PEER group sessions (50-60 minutes): The procedures for this are the same as for Aim 2. Only those in the PEER condition attend PEER group sessions. PEER group sessions may be delivered via phone/video.

7) Other support: The procedures for this are the same as for Aim 2, except that for those randomized into the ESFT condition, support will be provided by non-peer staff.

8) PEER graduate groups (50-60 minutes): Optional monthly graduate groups will be offered to participants in the PEER condition once they complete the weekly groups described above. The group will be facilitated by the same peer support specialist(s) who lead the PEER group to provide extra support for veterans during the second phase of the PEER intervention. PEER graduate groups may be delivered via phone/video. Once the veteran completes the second phase of the intervention they will no longer be able to attend the graduate groups.

9) Time point 2 assessments (120-180 minutes): At time point 2 (~12 weeks after randomization), Veterans will complete another set of assessments including questionnaire/interview measures of physical activity, mobility, self-efficacy, social support, psychiatric symptoms, cognition, quality of life, and/or functioning. Veterans will be paid \$50 for these assessments and it can be split into multiple appointments if needed. Parts of this assessment may be completed via phone if meeting face-to-face is not feasible and/or if meeting face-to-face would result in a delay in gathering the data. Measures of physical activity may be repeated at an additional visit if necessary.

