Follow-up phone interview- 30-60 minutes

*Aim 3 (n=20): Participants engage in the following study activities over ~30 weeks. Consent, screening, and assessments will be spread over multiple visits as needed.
Consent- 60 minutes
History and physical and blood draw (as needed)- 60 minutes
Baseline assessment and randomization- 120-180 minutes
PEER/ESFT individual sessions- 60-120 minutes
GeroFit supervised fitness training sessions- ~60 minutes/day, three days/week, for 24 weeks
PEER group sessions- ~60 minutes/week for first 12 weeks of study participation
PEER graduate groups (optional) - ~60 minutes/month for second 12 weeks of study participation
Time point 2 assessments- 120-180 minutes
Time point 3 assessments - 60-120 minutes

Qualitative interview (n=15-20)- 60-120 minutes

Follow-up qualitative interview for Aim 2 and Aim 3 participants - approximately 60 minutes

Aim 4 (n=18):
180-240 minutes for consent and assessment battery

4 *** Describe the amount of time it will take to complete the entire study:**

Aim 1: 1 year
Aim 2: 1 year and 3 months
Aims 3 and 4: 2 years and 9 months

Total duration: 5 years

5 *** Describe any additional participant requirements:**

N/A

Sample Size and Data Analysis

If you uploaded a separate research protocol document in the 'Research Protocol' page, cite the applicable section and page numbers from that document in the answer boxes below.

1 * Provide the rationale and sample size calculations for the proposed target population:

For the open trial (Aim 2), we aim to recruit 6 older Veterans with psychotic disorders to establish acceptability and perceived utility of the PEER intervention.

For the pilot randomized controlled trial (Aim 3), we aim to recruit 20 older Veterans with psychotic disorders to establish feasibility and preliminary efficacy of the PEER intervention compared to the ESFT condition. All participants (n=20) will be invited to participate in qualitative interviews.

For Aim 4, we aim to recruit 18 older Veterans with psychotic disorders to complete in-depth assessments of health and functioning.

Across Aims 2, 3, and 4, following initial chart screening, we estimate that we will enroll 60 participants. With these 60 participants, additional screening procedures will be conducted, and some participants will no longer be eligible. Then we will have final sample sizes of 6 for Aim 2, 20 for Aim 3, and 18 for Aim 4.

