2 * Provide the plan for data analysis. Include in the description the types of comparisons that are planned (e.g., comparison of means, comparison of proportions, regressions, analysis of variance, etc.), which is the primary comparison/analysis, and how the analyses proposed will relate to the primary purposes of the study:

Aim 2: We will conduct qualitative analysis of in-person and phone interview data. Interview audio files will be transcribed verbatim. After transcription, participants' comments will be compiled to summarize acceptability and perceived utility of each of the components of the PEER intervention.

Aim 3 (quantitative):

PEER intervention feasibility will be measured using descriptive statistics, including:

- (a) rates of engagement (# who attended at least three PEER group sessions after the engagement session divided by # randomized to PEER)
- (b) attendance of group sessions (percent of participants who engaged in PEER who attend 50% or more of PEER group sessions)
- (c) treatment dropout rates (# who dropped out prior to completing the intervention divided by # who engaged)

PEER intervention preliminary efficacy will be tested by comparing the PEER condition and the ESFT condition on a number of outcomes, including:

- (a) Attendance of supervised fitness training sessions, i.e., the number of times participants attended supervised fitness training sessions, including both peer-attended and independent visits. Group mean counts of attendance at the fitness training sessions during the intensive period will be compared using a Poisson or Negative Binomial regression model with treatment condition as the primary independent variable.
- (b) Ambulatory physical activity, i.e., total number of step-counts for one week, measured by pedometer. We will use an ANCOVA model to compare mean step-count at TP2, adjusting for baseline measurement (TP1).
- (c) Maximal aerobic capacity, measured by Graded Exercise Treadmill Test, using ANCOVA in the same way as in (b).
- (d) Other outcomes, including self-reported physical activity, MPPT, 6-MWD, and VR-36 Physical Component Score.
- (e) We will assess the maintenance of treatment effects at TP3 by comparing group means at TP3 using a two-time-point repeated outcomes model (TP2 and TP3) while continuing to adjust for baseline value.
- (f) Exploratory analyses will be conducted to identify potential mediators and moderators of treatment.

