
Peer Education on Exercise for Recovery (PEER):

In Aim 2, all participants will participate in PEER. In Aim 3, half the participants will be randomized to participate in PEER. PEER is a peer-delivered, group-based coaching intervention, which will promote participation in supervised fitness training and everyday physical activity. PEER will consist of a 12-week intensive phase and a 12-week maintenance phase. The intensive phase will consist of one-on-one individual sessions with a peer coach, 12 weekly PEER group sessions led by a peer coach with a focus on education/goal-setting/action planning, and other support such as phone call reminders/prompts from the peer coach. The 12-week maintenance phase will include continued, stepped down support from the peer coach. All components of PEER may be delivered by phone/video.

Enhanced Supervised Fitness Training (ESFT; Aim 3 only):

In Aim 3, half the participants will be randomized to participate in ESFT. ESFT will provide individual support from non-peer research staff, to promote participation in supervised fitness training and everyday physical activity. ESFT will consist of individual session(s) and other support such as phone call reminders/prompts from a non-peer research staff member, over a 24-week period. All components of ESFT may be delivered by phone/video.

ID: VIEW4E0BC12A9F800
Name: v2_Behavioral Interventions

Testing

You indicated that this study involves neuropsychological or psychophysiological testing.

If you uploaded a separate research protocol document in the 'Research Protocol' page, cite the applicable section and page numbers from that document in the answer boxes below.

1 * List all of the tests to be used in the study, including both standardized and non-standardized assessments:

Repeatable Battery of Assessment for Neuropsychological Status (RBANS)
TRAILS A (TMT A)
UCSD Performance-Based Skills Assessment - Brief Version (UPSA-B)

2 * Describe procedures related to all testing:

The RBANS is a comprehensive neuropsychological screening battery for individuals with SMI. In Aim 3 the pilot randomized controlled trial, the RBANS will be completed at baseline and time point 2. In Aim 4 it will be completed one time. It will take about 30 minutes to complete. For participants completing this assessment by phone/video, a limited set of subtests will be completed.

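### PEER is delivered in groups and ESFT individually, but the named models have no group term; if outcomes within PEER groups are positively correlated, standard errors will be too small

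*Combined protocol and SAP*

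**What the plan says.** The sample size statement (Sample Size and Data Analysis, item 1) reads: "For the pilot randomized controlled trial (Aim 3), we aim to recruit 20 older Veterans with psychotic disorders". Behavioral Intervention, item 1, splits them evenly: "In Aim 3, half the participants will be randomized to participate in PEER" and "In Aim 3, half the participants will be randomized to participate in ESFT". That is about 10 per arm.

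The arms differ in format. Study Procedures, item 1, Aim 3 states: "Participants will be randomized to receive group-based peer coaching (the PEER condition) or individual support from non-peer staff". It adds: "Only those in the PEER condition attend PEER group sessions". Behavioral Intervention, item 1, describes the experimental arm this way: "PEER is a peer-delivered, group-based coaching intervention, which will promote participation in supervised fitness training and everyday physical activity". Of the comparator it says: "ESFT will provide individual support from non-peer research staff".

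The analysis plan (Sample Size and Data Analysis, item 2, Aim 3 quantitative) names these models:

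- (a) supervised training attendance: Poisson or negative binomial regression on treatment condition.
- (b) step count: "We will use an ANCOVA model to compare mean step-count at TP2, adjusting for baseline measurement (TP1".
- (c) maximal aerobic capacity: the same ANCOVA.
- (d) other outcomes: no model named.
- (e) maintenance at time point 3: a two-time-point repeated outcomes model, adjusted for baseline.

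The documents contain no group or facilitator term, cluster-robust standard error or ICC. They do not give the number or size of PEER groups, whether membership is closed or rolling, the number of coaches, or an alpha level.

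**The concern.** People who attend the same weekly group share a leader, a discussion and each other's example. Their attendance and activity may therefore be more alike than those of two people supported separately. The named models default to independence between people. Under positive within-group correlation, the PEER mean is less precise than the model reports, and one cohesive or disrupted group can resemble a treatment effect.

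This matters because the plan goes beyond description. Preliminary efficacy is to be tested, and the research design section hypothesizes that differences will still be significant at the end of the maintenance phase. With about 10 people in PEER, one or two groups is a plausible layout, and that is where the effect is largest.

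**Working it through.** The plan has no figure to reproduce: the target of 20 comes without alpha, power, effect size or ICC.

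**Inputs from the documents:** 20 people, half per arm; groups in PEER only; ANCOVA with one baseline covariate, so residual df = 20 − 3 = 17.

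**Assumptions:** two-sided 5% level; closed groups; ICC of 0 to 0.2 in PEER and none in ESFT; four possible layouts of 10 people.

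**Step 1, formula.** The PEER design effect is 1 + (m − 1) × ICC, where m is the size-weighted mean group size. For groups of 3, 3 and 4, m = (9 + 9 + 16)/10 = 3.4. With equal arms, the variance of the arm difference is multiplied by [2 + (m − 1) × ICC]/2, and its standard error by the square root of that.

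| PEER layout | m | SE factor, ICC 0.05 | ICC 0.1 | ICC 0.2 |
|---|---|---|---|---|
| Five pairs | 2 | √1.025 = 1.01 | √1.05 = 1.02 | √1.10 = 1.05 |
| 3, 3, 4 | 3.4 | √1.06 = 1.03 | √1.12 = 1.06 | √1.24 = 1.11 |
| Two of 5 | 5 | √1.10 = 1.05 | √1.20 = 1.10 | √1.40 = 1.18 |
| One of 10 | 10 | √1.225 = 1.11 | √1.45 = 1.20 | √1.90 = 1.38 |

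**Step 2, simulation.** No treatment effect, baseline-outcome correlation 0.6, ANCOVA ignoring groups, 60,000 trials per cell. Type I error:

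| PEER layout | ICC 0 | 0.05 | 0.1 | 0.2 |
|---|---|---|---|---|
| Five pairs | 5.1% | 5.4% | 5.7% | 6.3% |
| 3, 3, 4 | 5.1% | 5.7% | 6.3% | 7.8% |
| Two of 5 | 5.2% | 6.2% | 7.2% | 9.7% |
| One of 10 | 5.0% | 7.5% | 10.3% | 15.9% |

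A repeat with baseline correlation 0.5 and 40,000 trials gave, at ICC 0.1 and 0.2, 5.3% and 6.2% for pairs, 6.3% and 7.8% for 3, 3, 4, 7.5% and 9.8% for two fives, and 10.4% and 15.7% for one group of 10.

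**Step 3, cross-check by t distribution.** For two groups of 5 at ICC 0.1, the simulated ratio of true to model standard error is 1.10. The critical value 2.110 then acts as 2.110/1.10 = 1.918 on 17 df, a two-sided tail of 7.2%. For one group of 10 at ICC 0.2, the ratio is 1.427, so 2.110/1.427 = 1.478 and the tail is 15.8%. Both agree with the second table. The ratio of 1.427 exceeds the formula's 1.38 because the model's residual variance also misses part of the shared component.

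**Step 4, would fitting the group variance solve it?** A test on PEER group means with Satterthwaite df gives 4.7 to 4.8% for five pairs. For two groups of 5 it still gives 6.0% (ICC 0) to 7.3% (ICC 0.2), on a median of about 4 to 6 df. With one group the variance cannot be estimated.

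**Step 5, would a fixed-ICC correction?** Multiplying the PEER-arm variance by the design effect at the true ICC (0.1 or 0.2) gives 5.0 to 5.5% in the multi-group layouts, and 5.5% and 6.0% for one group of 10.

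**The case against.** The strongest reply is that the inflation is conditional. A reader might infer that the standard errors are wrong and that false positives exceed the nominal rate. The documents do not support that as a fact: they state no ICC, group size or nominal rate, and at ICC 0 nothing happens. At ICC 0.05 the simulated error is 5.4 to 7.5%. This stands, and the point is worded accordingly.

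Second, membership may be rolling. Group sessions are tied to each person's own first 12 weeks, and Aims 3 and 4 together run 2 years and 9 months. With rolling entry, m is only approximate and the layouts above are illustrations. This also stands.

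Third, the mechanism should not be overstated. Reminders and prompts are given in both arms, and PEER includes one-on-one sessions, so the share of any effect carried by the groups is unknown. Nor can ESFT be presumed independent, since one staff member may support several people there.

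Fourth, proportion. This is a 20-person pilot; 10 per arm needs a difference of about 1.3 SD for 80% power. For outcome (a), a simulation assuming a mean of 15 visits and dispersion 0.3 gave 39 to 42% false positives under Poisson with no group effect at all. That is a separate and larger risk. It limits the weight of the present point but does not answer it.

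**Conclusion.** The gap is real and its consequence is conditional. The design is partially nested, and the models named for (a), (b), (c) and (e) make no allowance for it. If outcomes within PEER groups are positively correlated, intervals and p-values will be too optimistic. For ANCOVA, the effect is negligible at ICC 0 and small for pairs. At ICC 0.1 and 0.2 it reaches about 7% and 10% for two groups of 5, and about 10% and 16% for one group of 10. These figures rest on an assumed two-sided 5% level, closed groups and assumed ICCs. They were not derived for the count model in (a) or the repeated-outcomes model in (e), and (d) has no named model to assess.

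A reader might also conclude that a fitted group effect is required, or that an efficacy statement should have to survive a particular ICC. Neither follows. With one or two groups the variance is poorly estimated or not estimable, and the documents offer no basis for a pass/fail ICC. The point is a cheap improvement to the analysis.

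**What to change.** 1. State the planned number and size of PEER groups, whether membership is closed or rolling, and the number of coaches and ESFT support staff.
2. Record each PEER participant's group, and the coach or support staff member for every participant in both arms. This may be hard to reconstruct afterwards.
3. Keep the planned models. Beside each PEER-ESFT estimate for (a) to (c), (e) and whatever model is chosen for (d), report sensitivity intervals at fixed ICCs of 0, 0.05, 0.1 and 0.2, with the PEER-arm variance multiplied by 1 + (m − 1) × ICC and m the size-weighted mean group size. For the count model, apply the inflation to the variance of the PEER log rate.
4. If there is only one group, state that group and arm effects cannot be separated. If membership is rolling, state that m is approximate. Name either as a limitation.

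The cost is two recorded variables and a short paragraph of analysis text. The sensitivity intervals are wider: for groups of three or more, by about 6 to 20% at ICC 0.1 and 11 to 38% at ICC 0.2, depending on group size; for pairs, by about 2% and 5%. The main estimates do not change.
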